### **13.4 Consent Process: Revised Common Rule, Section 219.116: General requirements for informed consent, whether written or oral, are set forth in this paragraph and apply to consent obtained in accordance with the requirements set forth in paragraphs (b) through (d) of this section. Broad consent may be obtained in lieu of informed consent obtained in accordance with paragraphs (b) and (c) of this section only with respect to the storage, maintenance, and secondary research uses of identifiable private information and identifiable biospecimens.**

Are you requesting a waiver or alteration of informed consent?

Yes  No

Please explain the consent process:

Once patients have been prescreened and approached, patients will be shown to a private room to review the consent form with the researcher. The researcher will lead patients through the consent form using proper consenting procedures, then give patients time to further review the consent form privately and receive answers to any questions they may have regarding the study. Patients will be granted as much time as they need to make their decision in a private space. The patient will decide whether to participate, and will sign and date the consent form along with the researcher. The participant will also receive a duplicate copy of the consent form, signed and dated by the researcher.

### **13.5 DoDI 3216.02 requires an ombudsman to be present during recruitment briefings when research involves greater than minimal risk and recruitment of Service members occurs in a group setting. If applicable, you may nominate an individual to serve as the ombudsman.**

N/A  
 Propose ombudsman

### **13.6 Withdrawal from Study Participation:**

Explain the process for withdrawal and specify whether or not the subjects will be given the opportunity to withdraw their data their data/specimens in the event they wish to withdraw from the study

Participants may contact a member of the research team using any of the contact methods on the ICF to let them know that they wish to withdraw. They will be prompted to revoke their HIPAA Authorization as well, and have instructions recapitulated.

Once we have received the participant's revocation of HIPAA Authorization, their data will be purged from the study.

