## 11.0 Statistical/Data Analysis Plan

### 11.1 Statistical Considerations:

List the statistical methods to be used to address the primary and secondary objectives, specific aims, and/or research hypotheses. Explain how missing data and outliers will be handled in the analysis. The analysis plan should be consistent with the study objectives. Include any sub-group analyses (e.g., gender or age group). Specify statistical methods and variables for each analysis. Describe how confounding variables will be controlled in the data analysis

The characteristics of subjects including demographics and questionnaire responses will be summarized using descriptive statistics (e.g. mean  $\pm$  standard deviation for continuous variables, and counts (%) for categorical variables). Alternatively, response frequencies for the questionnaires will be determined and displayed in tabular and graphic formats. After examining the response frequencies, some variable categories will be collapsed in order to allow further analysis using them as dependent measures in subsequent analysis (chi-square and logistic regression analyses). For the continuous outcomes (quantitative measurements such as Pain Disability Index scale, self-efficacy, positive outcome expectations, catastrophizing, fear avoidance beliefs and distress in Aims 2 and 3), we will conduct the Kolmogorov-Smirnov or the Shapiro-Wilk test to confirm the normality prior to performing statistical analyses. We will detect outliers via histograms, box-plots, normal plots and summary statistics. Where appropriate, we will conduct logarithmic transformation on variables.

All analyses will be conducted using the principle of "intent-to-treat" in which every participant is assumed to have received his/her assigned intervention, regardless of adherence.

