**Table 2. Sample size and power**

Cohort size N (Total sample)	Loss to follow-up or noncompliance	Unpaired t- test	Fisher exact test			
			Effect size 	Power (%)	Effect size 	Power (%)
117 (234)	40%				0.30 (p1=0.8, p2=0.50)	95.4
100 (200)	30%	0.5	83.6			
167 (334)	40%				0.25 (p1=0.8, p2=0.55)	95.8
143 (286)	30%	0.5	94			
250 (500)	40%				0.20 (p1=0.8, p2=0.6)	96
215 (430)	30%	0.4	93.2			
334 (668)	40%				0.15 (p1=0.8, p2=0.65)	96
286 (572)	30%	0.3	84.9			

1 standardized mean difference of 2 groups  
2 absolute proportion difference of 2 groups with proportions ( $p_1 = P(\text{above MID in pre-training cohort})$ ,  $p_2 = P(\text{above MID in post-training cohort})$ )

**Missing data:** We will make every effort to prevent and avoid missing data. Even with the most robust processes, however, some missing data is inevitable. We will assess the mechanism of missing data by comparing patients with and without missing values on baseline and other complete information, to detect any patterns in demographics or other characteristics associated with missing data. First, the various missingness assumptions (missing completely at random: MCAR, missing at random: MAR or missing not at random: MNAR) will be tested by comparing subjects with missing and non-missing data. In order to incorporate uncertainty in handling missing data, we will perform a multiple imputation, which begins with a prediction of the missing data using the existing data from other variables. The missing values will then be replaced with the predicted values, and a full data set called the imputed data set will be created. This process iterates the repeatability and makes multiple imputed data sets. Each multiple imputed data set produced will be then analyzed using the standard statistical analysis procedures for complete data, and give multiple analysis results. Subsequently, by combining these analysis results, a single overall analysis result will be produced.

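### Section 13.6 prompts withdrawing participants to revoke HIPAA Authorization and purges the data of those who do, which is not reconciled with the intent-to-treat, missing-data and baseline-comparison plans

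*Combined protocol and SAP*

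**What the plan says.** Section 13.6 (Withdrawal from Study Participation) sets out a sequence. A participant tells the research team that he or she wishes to withdraw. Then: "They will be prompted to revoke their HIPAA Authorization as well, and have instructions recapitulated". Then: "Once we have received the participant's revocation of HIPAA Authorization, their data will be purged from the study". The section describes no route by which a participant stops the surveys and leaves the records already collected in place, and it asks for no count of the records removed.

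The analysis sections assume that those records exist:

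- Section 11.1 applies intent-to-treat to all analyses, under which "every participant is assumed to have received his/her assigned intervention, regardless of adherence".
- Section 11.6 (missing-data paragraph after Table 2) will examine the missingness mechanism by "comparing patients with and without missing values on baseline and other complete information", and will then impute missing values from each participant's other variables.
- Section 9.3, Aim 2, compares baseline risk factors between the two cohorts. Section 10.1 has the baseline battery completed before the next appointment, so this comparison should not depend on who stays to 12 months.

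**The concern.** A participant's right to have data removed is not in question. The difficulty is that revocation is put to everyone who announces a withdrawal, as the next step, when many of them may only want the surveys to stop. A participant who leaves late in follow-up and accepts the prompt loses the baseline battery and every completed follow-up as well as the questionnaires still to come.

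For those participants the missing-data plan has nothing to work with. They cannot be compared with stayers at baseline, they cannot be imputed, and they drop out of Aim 2. In a non-randomized comparison of two sequential cohorts, equal withdrawal in the two phases cannot be presumed. Sections 14.1 and 14.6 also give a plausible link to outcome: some participants may find the mental health questions distressing, and high baseline scores are notified to the therapist and the research monitor. Distress is itself a study outcome. If loss were related to distress and differed by phase, the purge would remove the records needed to see it.

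**Working it through.** **1. Does the purge create a sample-size error?** The inputs are in 11.5, 11.6 and Table 2: standardized difference 0.3, two-sided alpha 0.05, 1:1 allocation, 30% loss.

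- Table 2: 286 × 0.7 = 200 per cohort. A two-sample t-test (noncentral t) gives 84.9% power, which is the figure in Table 2.
- Requested size: 300 × 0.7 = 210 per cohort, giving 86.6%.

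Participants who withdraw before completing follow-up are already inside the 30% allowance, so the purge does not change the planned completer power.

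**2. What does change?** The set available for intent-to-treat and imputation. Expected attrition is 300 × 0.30 = 90 per cohort. The share of these who would revoke is not in the documents, so it is assumed:

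| Share of the 90 who revoke (assumed) | Purged per cohort | Left per cohort |
|---|---|---|
| 0% | 0 | 300 |
| 10% | 9 | 291 |
| 25% | 22.5 | 277.5 |
| 50% | 45 | 255 |

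Expressed as a share of all enrolled, 2% to 5% (assumed) is 6 to 15 of 300 per cohort.

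**3. How large could the bias be?** Let p be the proportion purged in a cohort and g the amount, in SD, by which the purged participants' mean outcome is worse than that of the retained. The full-cohort mean is then the retained mean minus p × g, so the retained mean is too favourable by p × g. With the same g in both cohorts and no true difference:

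bias = g × (p in post-training cohort − p in pre-training cohort)

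All values of p and g below are assumed.

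| p pre-training | p post-training | g (SD) | Bias (SD) | Share of the 0.3 design effect |
|---|---|---|---|---|
| 5% | 5% | any | 0 | 0% |
| 3% | 7% | 0.5 | 0.5 × 0.04 = 0.02 | 0.02 / 0.3 = 7% |
| 5% | 10% | 0.5 | 0.5 × 0.05 = 0.025 | 8% |
| 5% | 15% | 0.25 | 0.25 × 0.10 = 0.025 | 8% |
| 5% | 15% | 1.0 | 1.0 × 0.10 = 0.10 | 33% |

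The last row needs a large imbalance in revocation and a large outcome gap together.

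**4. How much of that would keeping the data recover?** For records collected before withdrawal (the baseline used in Aim 2 and any completed follow-up), all of it. For outcomes due after withdrawal, only what the earlier records can predict through imputation, because those outcomes are missing either way. Each bias figure is therefore an upper limit on the gain under its assumptions.

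**The case against.** The strongest reply is that the rule is narrow, and several stronger readings that a reader might draw from 13.6 do not hold.

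- *Withdrawal deletes the data.* It does not. The purge waits for a received revocation, and a participant who withdraws and ignores the prompt triggers nothing.
- *Dropouts in general are removed.* They are not. All follow-up is remote (10.1, 14.5), so a participant can leave simply by not answering. Such participants keep their records and remain in the comparison and imputation of 11.6. They may well be most of the expected 30%, although the documents do not say.
- *Every trace is purged.* De-identified SOAP notes carry no Subject ID (10.2, SOAP Note Review), so they cannot be traced to a person who revokes.
- *The plan contradicts itself on intent-to-treat.* Section 11.1 words the principle around adherence and is silent on removal of data. The passages are unreconciled, but they do not contradict each other in terms.
- *The loss is non-random.* No section gives withdrawal rates, revocation rates or reasons. The link to distress is plausible but not established.
- *Removals cannot be counted.* Nothing in 13.6 forbids a tally. It just does not ask for one.

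The consent form and the HIPAA Authorization were also not available for this review. They may govern what can be kept, and may already separate stopping participation from removing data. It is fair to add that making data removal explicit is a considerate choice toward service members who answer depression, anxiety and PTSD scales.

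All of this stands, and it limits the point to participants who revoke. For them the objection leaves the gap open: 13.6 makes revocation the prompted step, the analysis sections need the records it deletes, and no section says how the two fit together.

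**Conclusion.** The point holds as an unreconciled gap of probably small effect, worth closing because closing it is cheap. It concerns only participants who contact the team, withdraw and revoke. It is not a sample-size error, and the documents do not show that any bias will occur.

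Bias depends on revocation being related to outcome and on the rate or the outcome gap differing between cohorts. With 3% against 7% and a 0.5 SD gap, all assumed, it is at most about 0.02 SD, or 7% of the design effect. Over the wider assumed range it runs from zero to 0.10 SD. What is certain under the present text is narrower: whoever revokes disappears from the intent-to-treat set, the missing-data comparison, the imputation and Aim 2, and the plan requires no record of how many did so in each phase. Purged records cannot be recovered later, so the change helps only participants who have not yet withdrawn when it is made.

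**What to change.** Amend 13.6 as follows:

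1. Remove the default prompt to revoke.
2. Make the default on withdrawal no further contact and no further surveys, with data already collected kept.
3. Tell the participant that removal of data already collected is also available on request, and act on it when asked. What may be kept is subject to the terms of the consent form and HIPAA Authorization and to IRB approval, so check those documents first and align them if needed.
4. Keep a non-identifying count of removals by phase and by last completed time point, and report it beside the missing-data comparison in 11.6.

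The cost is an IRB wording amendment and a slightly longer explanation at withdrawal. Participants lose no right.

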## 14.0 Risks and Benefits

### 14.1 Risks of Harm:

Identify all research-related risks of harm to which the subject will be exposed for each research procedure or intervention as a result of participation in this study. Consider the risks of breach of confidentiality, psychological, legal, social, and economic risks as well as physical risks. Do not describe risks from standard care procedures; only describe risks from procedures done for research purposes

As with most studies, there is a risk of breaches of privacy and/or confidentiality.

Additionally, during our initial questionnaire we ask our participants to self-report on a number of psychological and social health measures, notably depression, anxiety, and PTSD. It is possible that some participants may become distressed while answering these questions. If a participant experiences an emergent mental health event, the researcher will immediately contact a clinician to transfer the patient to the Emergency Medicine Department (EMD).

### 14.2 Measures to Minimize Risks of Harm (Precautions, safeguards):

For each research procedure or intervention, describe all measures to minimize and/or eliminate risk of harms to subjects and study personnel

We will minimize risks of confidentiality and privacy breaches as described in Sections 14.3 and 14.5, respectively.

We will address the potential for distress by informing patients of the nature of the questionnaires during the consenting process. Additionally, the survey tools we use to measure aspects of mental health are established, validated clinical psychology measures. If a participant grows distressed while responding to the questionnaire, we will notify their physical therapist, who may refer them to the adult mental health department or the emergency department, depending on the severity and urgency of the incident.

### 14.3 Confidentiality Protections (for research records, data and/or specimens):

Describe in detail the plan to maintain confidentiality of the research data, specimens, and records throughout the study and at its conclusion (e.g., destruction, long term storage, or banking). Explain the plan for securing the data (e.g., use of passwords, encryption, secure servers, firewalls, and other appropriate methods). If data will be shared electronically with other team members/collaborators outside the institution, describe the method of transmission and safeguards to maintain confidentiality. Explain whether this study may collect information

that State or Federal law requires to be reported to other officials or ethically requires action, e.g., child or spouse abuse

Electronic study data will primarily be housed on government furnished equipment, and files containing PII will be password protected. All data transmitted to NYU personnel will be de-identified and transmitted via SAFE. Paper forms such as consent forms and questionnaires will be secured in locked cabinets behind at least one additional locked door. The consent forms and intake forms, which contain identifiers, will be stored in a separate cabinet from any paper questionnaires.

We will be collecting data on distress, depression, anxiety, and PTSD. While any one of these measures may not be reportable, if our team psychologist believes these indicate a dangerous situation, e.g. a suicide risk, we will report to the appropriate authorities.

#### **14.4 Potential Benefits:**

Describe any real and potential benefits of the research to the subject and any potential benefits to a specific community or society

If the individuals in the research are considered experimental subjects (per 10 USC 980), and they cannot provide their own consent, the protocol must describe the intent to directly benefit all subjects

Participants will not directly benefit, but we expect to improve physical therapy for ADSM with musculoskeletal disorders.

#### **14.5 Privacy for Subjects:**

Describe the measures to protect subject's privacy during recruitment, the consent process, and all research activities, etc.

Recruiting and consenting: We intend to rely on physical therapy staff to introduce us to eligible patients in their exam room after their evaluation session, so that participants can be briefed on the study in private. Interested patients will be provided a private space in the PT clinic to review the consent form and ask questions.

Participation: Participants may either complete their baseline questionnaire in person or online; all follow-up questionnaires will be completed remotely. If they choose to participate in person, they will complete the questionnaire in paper in the consenting area. The online method will consist of the research team sending a link to the online questionnaire via encrypted email to the address specified by the participant. The online questionnaire will be hosted on REDCap.

#### **14.6 Incidental or Unexpected Findings:**

Describe the plan to address incidental findings and unexpected findings about individuals from screening to the end of the subject's participation in the research. In cases where the subject could possibly benefit medically or otherwise from the information, state whether or not the results of screening, research participation, research tests, etc., will be shared with subjects or their primary care provider. State whether the researcher is obligated or mandated to report results to appropriate military or civilian authorities and explain the potential impact on the subject

While our study is observational and physical therapy is a lower-risk clinic, we will be viewing SOAP notes and administering mental health survey tools. Several members of our research team are physical therapists, and another is a psychologist. This puts us in a position to discover incidental findings of a two different natures.

**Misdiagnosis or mistreatment of MSD:** If the physical therapists on the research team conclude that a subject's MSD has been misdiagnosed or that their course of treatment is grossly inappropriate, they will pass that information along to the department head of physical therapy, so the matter can be brought to the attention of the participant's therapist. However, we only plan to do this if the patient is at risk of harm, not if the study team simply believes the course of treatment is sub-optimal.

**Mental Health dangers:** During our initial questionnaire, we ask our participants to self-report on a number of psychological and social health measures, notably PTSD, depression, and anxiety. If a participant scores  $>50$  on the PCL-M scale for post-traumatic stress disorder,  $>16$  on the CES-D scale for clinical depression, or  $>10$  on the GAD-7 scale for anxiety disorder (the thresholds for severe psychiatric disorder) at baseline, we will notify the participant's physical therapist and our research monitor to make a referral for appropriate treatment. If we find evidence of an emergent mental health issue, a researcher will immediately contact the participant's physical therapist to transfer the patient to the Emergency Medicine Department (EMD).

## 15.0 Study Monitoring

### 15.1 Your study requires either Data and Safety Monitoring Plan (DSMP) or a Data and Safety Monitoring Board (DSMB).

- DSMP
- DSMB
- Both
- Not Applicable

## 16.0 Reportable Events

### 16.1 Reportable Events: Consult with the research office at your institution to ensure requirements are met. Describe plans for reporting unexpected adverse events and unanticipated problems. Address how unexpected adverse events will be identified, who will report, how often adverse events and unanticipated problems will be reviewed to determine if any changes to the protocol or consent form are needed and the scale that will be used to grade the severity of the adverse event.

Consult with the research office at your institution to ensure requirements are met

- Describe plans for reporting expected adverse events. Identify what the expected adverse events will be for this study, describe the likelihood (frequency, severity, reversibility, short-term management and any long-term implications of each expected event)
- Describe plans for reporting unexpected adverse events and unanticipated problems. Address how unexpected adverse events will be identified, who will report, how often adverse events and unanticipated problems will be reviewed to determine if any changes to the research protocol or consent form are needed and the scale that will be used to grade the severity of the adverse event

We believe that the most likely adverse events are already described under "Incidental Findings" (Section 14.6). Beyond those, the most plausible adverse events we foresee are possible breaches of privacy and/or confidentiality and the potential distress of answering questions regarding mental health, which are also previously explored in Section 14.1.

Any reportable events, expected or not, will result in our team submitting a Note to File to the IRB within 24 hours of discovery. Serious adverse events and unanticipated problems will be reported to the Research Subject Protection Division within 24 hours. Similarly, any protocol violations will be reported within five business days. Other events such as non-serious adverse events and protocol deviations will be reported with the next continuing review unless they require a protocol modification. In that instance, the event will be reported alongside the modification.

Research staff will inquire whether any adverse events (AEs) have occurred at each in-person encounter with participants, and REDCap surveys will include instructions for contacting the research coordinator or PI if an AE has occurred. All research staff interacting with participants will maintain blank AE Log forms. Due to the large sample size and low risk, an AE Log will not be maintained for every participant, only those involved in an AE.

